1.4 Clinical Experience with the ExAblate MR Guided Focused Ultrasound Transcranial System

1.4.1 Clinical ExAblate Body System

1.4.1.1 ExAblate Body System for the treatment of Uterine Fibroids

The ExAblate 2000 system received FDA approval for the treatment of Uterine Fibroids in October 2004 (PMA # P040003). Furthermore, this system gained both AMAR authorization (Israel Ministry of Health) and CE (European and others) approval for the indication of treating Uterine Fibroids. Subsequent studies lead to a software upgrade and an enhanced sonication protocol. A further upgrade to the system to allow the transducer arm 3-dimensional movement is currently under IDE investigation as IDE G100127

1.4.1.2 ExAblate New Software Validation (IDE #G050221)

This was an FDA-approved study to validate the new ExAblate application software as well as the use of the ExAblate system with 3T MR scanners for the treatment of UFs. This was only a safety study. A total of 40 subjects were treated under this protocol IDE. The PMA-S was approved on February 27, 2007 under P040003/S002.

1.4.1.3 Enhanced Sonication Protocol (IDE #G060017)

This was an FDA-approved study to validate the new Enhanced Sonication feature of the ExAblate system, a detachable cradle, and several other modifications to the ExAblate 2000 system. This was a safety study only. A total of 50 subjects were treated under this protocol IDE. Following completion of this study, a full PMA supplement was submitted to FDA for review and approval [PMA# P040003]. Approval was granted on 12/22/2009 under PMA Supp P040003/S006. The system is marketed under the trade name ExAblate 2000/2100 and is indicated for use in treating symptomatic uterine fibroids.

1.4.1.4 Enhanced Sonication Post Marketing Study-P040003/S007

InSightec is currently recruiting subjects for a post-market study using the FDA approved enhanced sonication feature to demonstrate the safety of the enhanced sonication feature within current treatment guidelines of 100% individual fibroid ablation within established serosal and sacral treatment margins; this study has completed its enrollment. Data analyses and final report are in progress, and due for submission to the FDA in March-2013.

1.4.1.5 Validation of ExAblate UF V2 – IDE G100127.

InSightec is currently recruiting centers and initiating IRB review for study conduct in order to gain approval for the ExAblate Model 2100 Type 1.1 (also refer to as ExAblate

UF V2). This ExAblate system will be operated with a NEW Clinical Application SW utilizing the added 5th degree of freedom of the transducer (A/P movement) in its overall planning and treatment of the uterine fibroids. This study will enroll 106 subjects under IDE # G 100127.

1.4.1.6 ExAblate Body System for the treatment of Breast Cancer

InSightec conducted FDA approved clinical trials under IDE # G990184 and G990201 to evaluate the safety and efficacy of the ExAblate system in the treatment of breast carcinomas [81-83]. Both of these studies are now closed. Currently, InSightec has an FDA conditional approval for a new breast cancer phase-2 study (IDE # G060023).

1.4.1.7 ExAblate Ablation of Breast Fibroadenoma

InSightec conducted a feasibility FDA approved clinical trials under IDE # G930140 to evaluate the safety and efficacy of the ExAblate system in the ablation of breast fibroadenoma [2]. Under this study, a total of 11 subjects were treated. The results of this study showed that 8 of the 11 subjects who had ablations were either partially (>50%) or completely (>90%) successful. No adverse effects were reported, except for one case of transient edema in the pectoralis muscle two days after therapy.

Following this feasibility study, InSightec initiated an FDA approved pivotal protocol to study ExAblate ablation of Breast Fibroadenoma (IDE # G010225). A total of 110 subjects were approved for this trial, and only 27 subjects were treated before the study was closed for enrollment due to lack of subjects enrollment. No unanticipated adverse effects have been reported or detected by MRI. Clinically, acute pain and discomfort were tolerable, and no long-term complications occurred.

1.4.1.8 ExAblate Body System for the treatment of Prostate Studies – Investigational Feasibility Studies

Prostate cancer is the second leading cause of cancer death in men in the United States. Most prostate cancers grow slowly with a high survival rate past 10 years if it is still confined to the prostate. The current treatment methods (surgical, external beam radiation therapy and male hormone suppression therapy) have significant side effects, such as impotence, incontinence, post-radiation colitis, etc. Because prostate cancer is usually slow growing, active surveillance at 6 month intervals using a prostate cancer marker (PSA – prostate-specific antigen) has been a primary treatment option. A focal treatment that could destroy the cancerous cells without harming the neurovascular bundle could provide a more palatable treatment with fewer side effects and extend life expectancy from prostate cancer causes.

Feasibility studies have been performed outside the United States to demonstrate the ability of the ExAblate to successfully target the prostate gland and ablate it (Total Gland Ablation – TGA). Additionally studies are now underway using focal therapy to ablate only cancerous foci within the prostate and leave the remainder of the gland intact. The difficulty here is in the methods available to identify the cancerous foci. These cancerous foci are generally not visible on MRI or CT, so careful, methodical biopsy mapping with multiple cores (minimum of 12 cores, commonly 16 cores for larger glands) must be

performed in order to identify the portion of the gland with the cancer. In pilot studies with 14 subjects treated to date, the outcomes generally have demonstrated a minimal degree of sexual and urinary side effects (except for transient obstructive urinary symptoms) unless the cancerous foci involve the neurovascular bundles and the conscious decision is made to include them in the treatment region-of-interest. Subjects that are eligible for participation are those with slow cancer growth being followed with active surveillance or with Gleason score of 6 (3+3) and no more than 2 cancerous foci in two or fewer adjacent sectors that would be amenable to ExAblate treatment. To date, feasibility studies are underway in Russia, India, Singapore, Italy, and will soon start in Canada.

In the United States under FDA oversight, InSightec has received the full FDA approval under IDE # G100108) to initiate a feasibility study in the treatment of prostate cancer.

1.4.1.9 ExAblate Body System for the Palliative treatment of Metastatic Bone Tumors

First, InSightec performed FDA approved study for a feasibility study of ExAblate ablation of metastatic bone tumors under IDE # G050177. A total of 10 subjects were enrolled and treated at two (2) study sites. This study is now completed, and a final report was submitted to the FDA [84]. Most recently a PMA submission (PMA # P110039) with the pivotal study data was submitted to FDA on 5, DEC-2011.

1.4.1.9.1 Bone Feasibility Study IDE# G050177

The objective of this trial was to evaluate the safety and effectiveness of using ExAblate as a treatment for pain palliation in subjects with metastatic bone tumors. This study was designed as a prospective, one arm, non-randomized study. Ten subjects were enrolled at two sites. Nine subjects completed the study; one subject could not complete treatment due to limited device accessibility to the lesion.

Only 3 mild AEs were reported in the study with no device-related deaths, life-threatening injuries or permanent injuries, nor serious adverse events. There were 2 events of mild sonication-induced pain; both resolved the day that sonications ended. In addition, there was 1 event of a mild shivering reaction to conscious sedation lasting only a few minutes during the procedure with subsequent resolution. All of these events were anticipated side effects that were identified in the study protocol as possible treatment-related complications.

As noted above, effectiveness was measured by the level of pain relief (as measured by VAS), decrease in analgesics/opiate medication usage, and improved quality of life (as measured by SF-36). Prior to ExAblate treatment, the mean pain score was 5.6 ± 1.2 (N=10, score range: 4-7). A very rapid and sustained relief response was observed in subjects' pain relief. At 3 months, the mean score had dropped to 0.4 ± 0.6 (a 93% decrease from baseline). With respect to medication usage, all subjects maintained or decreased their medication usage.

Overall, these results demonstrate the safety and effectiveness of using ExAblate as a treatment for pain palliation in subjects with metastatic bone tumors.

1.4.1.9.2 Pivotal Bone Metastasis Study (IDE# G070022) – Brief Overview

InSightec received full approval for a phase-3 Pivotal study for the ExAblate treatment of bone metastases palliation (IDE # G070022). A total of 148 subjects were to be enrolled and treated at up to 20 sites. The pivotal clinical trial was a prospective, randomized (3:1), single-blind, sham-controlled, multicenter, two-arm study with sham-crossover option. Consistent with prior correspondence between the company and FDA, InSightec has conducted an interim analysis of study data, providing for a statistical penalty addressing the early look at the data, in order to initiate PMA approval for this indication. This interim analysis has been performed under the interim statistical analysis plan previously submitted to and approved by FDA (G070022/S54). The study objective is to evaluate the safety and effectiveness of an ExAblate thermal ablation treatment as compared to a sham treatment (where no energy is delivered) to reduce/relieve the pain of metastatic or multiple Myeloma bone tumors in subjects who are not suitable candidates for radiation therapy. The submission is under review at the Agency (PMA # P110039).

1.4.2 ExAblate Transcranial System

InSightec has two ExAblate Transcranial systems: mid (650 KHz) and low frequency (200 KHz). These 2 systems (medium and low range frequency) have two different characteristics:

1. Mid frequency: functional discrete lesioning for deep central locations; focal thermal lesions
2. Low frequency: tumor ablation and has wide treatment envelope

These differences are summarized in the following table:

| Table 1: Summary of main differences between the low and mid frequency ExAblate systems | |
|--|---|
| Low frequency ExAblate Transcranial System | Mid frequency ExAblate Transcranial System |
| Enables access to most of brain volume | Deep brain targets |
| Spot diameter: 4-12mm | Spot diameter: 2-6mm |
| Low frequency (~220kHz) | Medium frequency (~650kHz) |
| Support both standard and burst Sonication regimes | Support standard sonication only |
| 
Standard sonication delivers the required energy in a continuous fashion to the target
 
Burst Sonication: delivers the energy in a series of burst (high amplitude short duration of each burst of energy). The total accumulated energy is the same. The only difference is the way it is delivered to the target.
 | |

For the proposed study, the same mid-frequency ExAblate Transcranial system that was investigated for the treatment of Essential Tremor subjects (under IDE # G100169) will be used; it should be noted this same system is utilized for the FDA approved study for tremor in Parkinson's disease subjects. The system uses the same transducer, ALL clinical features and tools of this FDA ET IDE approved system version, subject interface and coupling, etc. There is no change to the thermal modeling, energy delivery, beam forming, nor treatment parameters and guidelines, and mitigating steps. Furthermore, the manufacturing process, device risk analysis, SW and HW verification and validation have also remained unchanged.

1.4.2.1 ExAblate Transcranial Treatment of Brain

1.4.2.1.1 Feasibility Study for Brain Tumor IDE # G020182 – ExAblate Transcranial Low Frequency System

In 2002, the FDA approved an IDE for a feasibility clinical study for the ExAblate Transcranial system in the treatment of brain tumors[48]. The purpose of this study is to evaluate the safety of MRI-guided focused ultrasound thermal ablation of brain tumors performed through intact human skull using the ExAblate system. Specifically, the objectives of this non-randomized study are:

- To evaluate the safety of FUS delivered through intact human skull to the brain, during the treatment, and during the follow-up period of 3 months.
- To evaluate the effect of thermal ablation in the target tumor with contrast MR imaging to identify viable tumor, and non-viable thermally ablated tissue

This study was limited to subjects with a newly diagnosed glioma, recurrent glioma, or metastatic cancer to the brain for whom surgery was felt to be not indicated by a physician not associated with the study.

Per FDA order under IDE # G020182/S02, this study was approved for a total of 10 subjects. Also, per same FDA order, a report was requested after enrollment and treatment of the first 3 subjects in order to gain the FDA approval for continuation.

- During these 3 treatments, all safety subsystems and monitoring of the device provided the intended safety monitoring capabilities. The adverse events that were captured were Non-Significant, Anticipated, Treatment Side Effects and incidental to the treatment.

The treatment of the 4th subject was done with an upgraded system (approved under IDE G#020182/S04). The treatment day safety was no different than those previously reported. The skull/dura temperature change was in the range of previous treatments. Utilizing the burst sonication regime, the designated tumor was completely ablated. This was consistent with our overall plan to achieve the efficacy needed.

1.4.2.1.2 ExAblate Transcranial MRgFUS system and Thalamotomy Procedures

The InSightec ExAblate TcMRgFUS system has been used in the thalamotomy treatment of neurological disorder such as neuropathic pain, essential tremor (“ET”), and Parkinson’s disease (“PD”) induced tremor. These studies were conducted under FDA IDE approvals (ET under IDE # G100169; enrolling for PD under IDE G # 120017), Health Canada (ET under Application # 166556), Swissmedic (NP001 study included Neuropathic pain, ET and tremor in PD subjects – Reference: 2011-MD-0001), and

Korean FDA (ET under KFDA Application # 260) oversights. Overall, more than fifty (50) subjects received the ExAblate TcMRgFUS thalamotomy procedure.

1.4.2.1.2.1 Study for Neuropathic Pain Outside the United States

The original study was an investigator initiated and sponsored study (Study number BZ001) in the treatment of neuropathic pain that was conducted at the University Hospital Zurich (Zurich Switzerland) using the InSightec ExAblate Transcranial (650 KHz) system. The study was approved by and performed according to the guidelines of the ethics committee of the University and the State of Zurich. At the conclusion of this study, an InSightec sponsored study was conducted under Swissmedic (Reference #: 2011-MD-0001) and local IRB approvals. This study (NP001) included subjects with Neuropathic pain, Essential tremor, and those subjects with Parkinson's disease induced tremor.

1.4.2.1.2.3 Study for Essential Tremor - Outside the United States

In addition to the Swissmedic study that included cohort of 1 subject (study is still on-going) with Essential tremor, InSightec conducted separate studies for the treatment of Essential tremor in both Canada and in Korea. A total of 8 subjects were treated to date as follows: 3 subjects in Canada, and 5 subjects in Korea. Both of these study protocol were similar to the FDA feasibility study (IDE G#100169). Overall, the ExAblate treatment safety profile is no different from the FDA feasibility study (for more details, see Section-1.4.2.1.2.4) nor from the safety profile of typical thalamotomy device procedures such as RF ablation and DBS. In short, safety events such as Dizziness and vomiting were reported, and both resolved without sequelae.

1.4.2.1.2.4 ExAblate Transcranial System Feasibility Study for Essential Tremor IDE - G100169

InSightec received FDA approval for a feasibility study of ExAblate Transcranial System for unilateral thalamotomy in the treatment of Essential Tremor under IDE # G100169. Fifteen subjects were enrolled and treated at one site and the study report was recently completed. Both the safety and effectiveness profiles showed a very favorable outcome of the ExAblate Transcranial MRgFUS treatment of patients with medication-refractory movement disorders, namely ET. The clinical outcomes subscales as well as the quality of life measures showed a substantial improvement in subject disabilities and their quality of life.

The incidence (number of patients experiencing an event) and severity of all device and procedure related AEs are summarized in Table 2. This list of events includes the non-significant and the significant anticipated treatment side effects as well as the events incidental to the treatment.

Table 2 Overall Adverse Events and Severity: ET-001

| | Event | Mild | Moderate | Severe | Total # of Events |
|------------------------------------|-------------------------|------|----------|--------|-------------------|
| Non-Significant Anticipated Events | Ache – pin site | 1 | 0 | 0 | 1 |
| | Balance | 7 | 0 | 0 | 7 |
| | Chest Pain | 1 | 0 | 0 | 1 |
| | Neural Deficit - speech | 2 | 0 | 0 | 2 |

Table 2 Overall Adverse Events and Severity: ET-001

| | Event | Mild | Moderate | Severe | Total # of Events |
|--|--------------------------------|-----------|-----------|----------|-------------------|
| | Neural Deficit – hand strength | 1 | 0 | 0 | 1 |
| | Emesis | 2 | 0 | 0 | 2 |
| | Fatigue | 3 | 0 | 0 | 3 |
| | Headache 1 Day | 4 | 5 | 0 | 9 |
| | Headache > 1 Day | 1 | 2 | 0 | 3 |
| | Numbness -- appendage | 1 | 0 | 0 | 1 |
| | Nausea | 2 | 4 | 0 | 6 |
| | Paresthesia - appendage | 3 | 0 | 0 | 3 |
| | Paresthesia - face | 4 | 1 | 0 | 5 |
| | light headedness | 7 | 1 | 0 | 8 |
| | Twitch | 1 | 0 | 0 | 1 |
| | Warm Sensation | 4 | 0 | 0 | 4 |
| | Edema | 1 | 0 | 0 | 1 |
| | Ataxia | | 1 | 0 | 1 |
| Non-Significant Subtotal | | 45 | 14 | 0 | 59 |
| Significant Treatment Anticipated Events | Balance | 2 | 2 | 0 | 4 |
| | Fatigue | 1 | 0 | 0 | 1 |
| | Infection – pin site | 1 | 0 | 0 | 1 |
| | Numbness – pin site | 1 | 0 | 0 | 1 |
| | Parasthesia - appendage | 1 | 1 | 0 | 2 |
| | Parasthesia - face | 4 | 1 | 0 | 5 |
| | Parasthesia - scalp | 4 | 0 | 0 | 4 |
| | Hypesthesia - scalp | 1 | 0 | 0 | 1 |
| | Burn – pin site | 1 | 1 | 0 | 2 |
| | Significant Subtotal | 16 | 5 | 0 | 21 |

Table 2 Overall Adverse Events and Severity: ET-001

| | Event | Mild | Moderate | Severe | Total # of Events |
|-------------------|----------------------------|-----------|-----------|----------|-------------------|
| Incidental Events | Sinusitus | 0 | 1 | 0 | 1 |
| | Bronchitus | 1 | 0 | 0 | 1 |
| | Incidental Subtotal | 1 | 1 | 0 | 2 |
| | Total | 62 | 20 | 0 | 82 |

The most significant results shown in Table 2 are that all these events are indeed anticipated events and were already identified as potential events in the study protocol. Furthermore, NONE of the adverse events reported to date were severe in nature. In fact, 76 % (62/82) were Mild events, and the remainder 24% (20/82) were Moderate. Most of these events resolved either the same day (49% of the total events) or within 2 weeks of treatment (26% of the total events). Hence, 61 events (i.e. 74%) resolved within 2 weeks of the procedure.

Of all the events that did not resolve within the first 2 weeks post procedure, 14 out of 82 events (17%) resolved in more than 2 weeks (not counting the incidental sinusitis (n=1)), and 7 events (9%) were reported as ongoing.

1.4.2.1.3 Overall summary of ExAblate TcMRgFUS safety profile

The safety events reported in all these studies present a favorable safety profile for brain surgery using the ExAblate TcMRgFUS for ablative therapy. The majority of all events are mild and transient. They generally fall into the pattern of other techniques indicating that these are generally the result of stereotactic device use (e.g., headache) and thalamotomy in general, regardless of the mechanism of therapy, due to brain tissue insult or due to heating of tissue locally surrounding the lesion target. The overall effectiveness profile was also shown to be very favorable.

2 OBJECTIVES

The objective of this prospective, randomized, double-blind (to subjects, local site and Tremor Core Lab assessors), crossover, multi-site, two-arm study (ExAblate treated arm Vs ExAblate Sham treated control arm) is to test the efficacy of treatment using the ExAblate Transcranial System and to further demonstrate safety in medication-refractory tremor in subjects with essential tremor (ET).

Safety: To evaluate the incidence and severity of adverse events (AE/AEs) associated with ExAblate Transcranial MRgFUS treatment of medication-refractory ET

Effectiveness: To determine the effectiveness of the ExAblate Transcranial MRgFUS treatment of medication-refractory tremor (i.e. ET). Efficacy will be determined utilizing the Clinical Rating Scale for Tremor (CRST) in ET from examinations at baseline and 3-Months post-ExAblate treatment.

- This study is designed as a prospective, randomized, double-blind (to subjects and Tremor Core Lab assessor), crossover, multi-site, two-arm study (ExAblate treated arm Vs ExAblate Sham treated control arm).

Assessments of primary efficacy endpoints will compare the three months after ExAblate treatment to Baseline measurements for clinical symptom relief. Safety of ExAblate in the treatment of ET will be collected for one year after ExAblate Sham or active treatment. Relative Safety will be evaluated using a common description of Significant Clinical Complications for patients treated in this study. This study will be performed on the 3T MR scanners.

Note:

It should be noted that the pre-market submission to the FDA will be performed following the completion of the 12 months follow up visit of the last Test Arm subject. This pre-market submission will be performed in full consultation with and approval of the FDA. However, per FDA order, all participating subjects will be consented for a total of 5 years.

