2.1 Primary Endpoints

2.1.1 Safety

Safety of ExAblate will be determined by an evaluation of the incidence and severity of device / treatment related complications from the first treatment day visit through ALL study follow ups. Adverse events (type, frequency, severity) are expected to be similar to those of previous studies using ExAblate TcMRgFUS for Thalamotomy

All AEs will be reported and categorized by investigators as definitely, probably, possibly, or unrelated to the device or procedure and categorized by treatment group / treatment arm.

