ALL imaging exams of this study must be forwarded to the Sponsor in a timely fashion immediately following their acquisition and properly anonymized from all subject identifiers.

4.2.2 Post-Treatment Follow-up – All procedures for follow-up are common between treatment groups..

4.2.2.1 Day 1 Follow-up Procedures:

The neurosurgeon will perform the following exams and make a decision as to whether or not to discharge the subject. Subjects who are found to be neurologically unstable will remain in the hospital until the neurosurgeon determines it is medically indicated to discharge.

- a) Review of medications
- b) physical exam
- c) neurological status

Any adverse events will be recorded and followed. The physician should treat the subject according to their best clinical judgment if adverse events are noted.

4.2.2.2 Week 1

The following evaluations should be performed at Week 1:

- Review of medications
- Physical exam

- Neurological status
- Adverse events
- Blinding form asking if they believe they received the actual treatment or the placebo treatment.

4.2.2.3 Month 1 and 3

The following evaluations should be performed at 1 & 3 months:

- Review of medications
- Physical exam
- Neurological Status
- CRST by blinded site assessor with taping for Central Lab assessment
- QUEST and PHQ-9-depression questionnaires should be completed by the subject
 - NOTE:

At any follow up visit, any subject who scores ≥ 20 on the PHQ-9 questionnaire, the subject should be referred out for psychiatric evaluation. The Columbia Suicide Severity Rating Scale, or like, may be used. Should there be a psychiatric treatment, then this psychiatric treatment should be recorded as an adverse event. A Copy of the psychiatric evaluation should become part of the CRF information as part of the adverse event outcomes and description. The investigator will evaluate whether the subject may continue participation in the study, or should be exited from the study for treatment

- Adverse events
- Blinding form asking if they believe they received the actual treatment or the placebo treatment.
- At Month 3,
 1. All subjects may be un-blinded after completing all Month 3 subject assessment measures.

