4.2.2.3.2 Reasons for Study Exit

In this study, subjects who opt for alternative treatments for Essential Tremor (not including medication change) at any point in the follow-up period will be exited from the study after completing required study examinations. The last set of evaluations prior to alternative therapy is considered the last study visit. The reason(s) for study exit will be noted on the Case Report Forms. No analyses of post alternative treatment changes are planned.

4.2.2.4 Month 6 and 12

To assess treatment long term safety and efficacy durability (i.e.: study secondary endpoint), follow up will also be completed at the 6 and 12 months post treatment. At these visits, all the data will be collected in the same fashion with videotaped tremor assessments as during the other visits, except that subjects and site assessor may no longer be blinded. These 6/12-Months videotapes must also be forwarded to the sponsor for storage.

The following evaluations should be performed at Month 6 and 12:

- Review of medications
- Physical exam
- Neurological status
- CRST (SBA unblinded) with videotaping,
- QUEST and PHQ-9-depression questionnaires should be completed by the subject
 - NOTE:

At any follow up visit, any subject who scores ≥ 20 on the PHQ-9 questionnaire, the subject should be referred out for psychiatric evaluation. The Columbia Suicide Severity Rating Scale, or like, may be used. Should there be a psychiatric treatment, then this psychiatric treatment should be recorded as an adverse event. A Copy of the psychiatric evaluation should become part of the CRF information as part of the adverse event outcomes and description. The investigator will evaluate whether the subject may continue participation in the study, or should be exited from the study for treatment

- Adverse events
- At Month 12 (ONLY), all subjects should undergo the following MR exams:
 - T2 weighted imaging

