6.4 Criteria for Removal from the Study

The investigator may withdraw subjects from the study as is deemed necessary or deemed to be in the best interests of the subject, such as,

- continued noncompliance with the protocol or study visits,
- severe illness or disability during the study for non-study issues,
- pursuit of subsequent alternative treatment for the same condition, or
- development of intolerable side effects where continued follow-up becomes too burdensome.

In addition, a subject may also chose to exit the study at any time, but will be strongly encouraged to participate in the follow-up visits for safety reasons (continued monitoring of subject safety).

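### Study exit can end adverse-event observation before the stated one year, and nothing requires non-serious events to be followed after an investigator- or protocol-driven exit

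*Protocol*

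**What the plan says.** Protocol section 2 (Objectives): "Safety of ExAblate in the treatment of ET will be collected for one year after ExAblate Sham or active treatment". Section 2.1.1 defines the primary safety endpoint as the incidence and severity of "device / treatment related complications from the first treatment day visit through ALL study follow ups".

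Three provisions allow or require a subject to leave earlier:

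- **Alternative treatment (4.2.2.3.2), mandatory.** The section says that "subjects who opt for alternative treatments for Essential Tremor (not including medication change) at any point in the follow-up period will be exited". Required examinations are completed first. Then: "The last set of evaluations prior to alternative therapy is considered the last study visit". No analysis of later changes is planned.
- **PHQ-9 of 20 or more (4.2.2.3, repeated in 4.2.2.4), discretionary.** After psychiatric referral, "The investigator will evaluate whether the subject may continue participation in the study, or should be exited from the study for treatment".
- **Side effects (6.4), discretionary.** One listed reason for withdrawal by the investigator is "development of intolerable side effects where continued follow-up becomes too burdensome".

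Section 6.4 urges continued safety visits, but the sentence concerns subjects who themselves choose to leave. Section 6.6 has ongoing events reviewed at subsequent visits, and it requires serious events to be documented to final outcome.

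In the SAP, section 5.1 puts every subject with at least one sonication in the Safety population. Section 7 does not impute safety data. Section 10.5 assigns an event with no resolution date to an Unresolved category.

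**The concern.** The plan states a fixed safety window, and then lets observation close early for reasons that can be related to how the subject is doing. A subject may look for another tremor treatment because this one did little. Psychiatric treatment or burdensome side effects may be a consequence of the procedure, though they need not be. If observation stops there, the loss is not clearly random.

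Two things are at stake. One is whether a non-serious deficit still open at exit later resolved. Permanent impairment is one of the four alternative criteria for a serious event in section 6.6, so an event that is non-serious at exit could qualify later without anyone being required to find out. The other is any new event between exit and Month 12, since no scheduled visit remains at which it would come to light.

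**Working it through.** **1. What each exit leaves in place**

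| Trigger | Status | Retained | Not required |
|---|---|---|---|
| Alternative tremor treatment | Mandatory | Events to the last evaluation before that therapy; the alternative treatment itself if it follows neurological change (6.3) | Resolution of open non-serious events; later events |
| PHQ-9 of 20 or more | Discretionary | Psychiatric treatment recorded as an adverse event, with the evaluation in the CRF | Same |
| Intolerable and burdensome side effects | Discretionary | The side effect, as an event before exit | Same |

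The SAP does not fill the last column. Its sensitivity analyses (10.6.6) repeat the primary efficacy analysis only, and the drop-out analysis in Protocol 5.7 compares baseline characteristics. The dropout listing in SAP 10.1 gives reasons, but on the ITT population, which needs a post-baseline value of the primary efficacy measure (5.2.1). The first such value is at Month 1.

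**2. The plan's own safety figures**

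Protocol 5.4 gives the probability of seeing at least one event, which is 1 − (1 − p)^n:

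- p = 0.05, n = 60: 0.954 (stated 0.95)
- p = 0.05, n = 45: 0.901 (stated 0.90)
- p = 0.05, n = 15: 0.537 (stated 0.52)
- p = 0.01, n = 60: 0.453 (stated 0.45)

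They reproduce to within 2 points. They assume that every subject is observed for the whole window.

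**3. Uncertainty in the persisting-deficit proportion**

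Inputs: 72 randomized at 3:1 (Protocol 5.4), so 72 × 3/4 = 54 ExAblate subjects. The number m of exits with unknown Month 12 status is an assumption, because the documents give none. The gap between counting all of them as resolved and all as persisting is m/54:

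- m = 1: 1/54 = 1.9 points
- m = 3: 3/54 = 5.6 points
- m = 5: 5/54 = 9.3 points

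These are upper limits. An exited subject whose deficit is a serious event should still have a documented outcome and would not widen the gap.

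**4. Effect on the chance of seeing an event**

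Let q, also an assumption, be the share of events that fall after exit and go unrecorded. The recorded rate is then 0.05 × (1 − q). With n = 45:

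- q = 0: rate 5%, probability 0.901
- q = 10%: rate 4.5%, probability 0.874
- q = 25%: rate 3.75%, probability 0.821
- q = 50%: rate 2.5%, probability 0.680

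Modest loss lowers the detection probability modestly. Only a large share of unrecorded events would change it much.

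**The case against.** A reader might infer that safety follow-up systematically ends in the subjects who do worst. The documents do not support that.

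- Two of the three exits are optional, and the side-effect criterion also requires that follow-up has become too burdensome.
- The mandatory exit is triggered by choosing another treatment, not by failed benefit. Bilateral tremor is permitted (3.1.1) and only one side is lesioned (4.2.1.1), so a subject with a good result could seek treatment for the other hand.
- Exited subjects stay in the Safety population with their earlier events. An undated event appears as Unresolved, so it is not counted as recovered.
- An exit for side effects follows an adverse event, so it cannot censor that subject on the event-free Kaplan-Meier curve.
- Permanence is not the only route to a serious classification, and 6.6 lets the DSMB settle borderline cases.

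All of this stands and limits the point. It does not remove it: Unresolved cannot separate a lasting deficit from one that cleared after exit, and it says nothing about later events.

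The long-term follow-up protocol (ET002-LTF) takes in all ExAblate-treated subjects and might recover some of them. However, its section 13.1.2 excludes those with a later intervention on the treated side, and sections 14.2 and 17.1 repeat the exit wording.

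It can also be said that events after another treatment are confounded. That is true, but it is a reason to show them separately rather than leave them uncollected.

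Nor should the 5.6 points in the working be set against the 5% in Protocol 5.4. That figure concerns seeing at least one event, not the precision of a persistence rate. The pilot's 7 ongoing events out of 82 (Protocol 1.4.2.1.2.4) show that some events last, but they count events and are not linked to exits.

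**Conclusion.** The point holds in a limited form. The one-year safety statement and the exit provisions do not fit together as written. For exited subjects, safety observation may end early, and no text requires non-serious events to be followed after an exit that the investigator or the protocol initiates. The missing information is how open non-serious events end and whether new events occur before Month 12.

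The size cannot be fixed from the documents. Under the assumption of 1 to 5 such exits among 54 ExAblate subjects, the proportion with a persisting deficit is uncertain by up to 1.9 to 9.3 points. This is a worthwhile, inexpensive improvement. The documents do not show that the safety results would be materially biased.

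**What to change.** The clinical exit rules are for the sponsor, but they must be reconciled with the one-year statement.

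- **Protocol 4.2.2.3, 4.2.2.4, 4.2.2.3.2 and 6.4:** distinguish leaving efficacy visits from leaving adverse-event collection. After an exit, continue to collect adverse events by telephone or chart at the scheduled visit times, to resolution or Month 12, unless consent is withdrawn. Flag events that start after an alternative treatment. The parallel wording in ET002-LTF 14.2 and 17.1 should follow.
- **SAP 10.5:** on the Safety population, tabulate exits by reason and arm. Give the proportion with deficits persisting at Month 12 twice: as observed, and with unknown outcomes counted as persisting. Show events after an alternative treatment separately.

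The cost is a few sentences, a few extra contacts and one table. The Objectives already say that subjects will be consented for five years, so contact to Month 12 is a modest request. The downside is that events after an alternative treatment are confounded and cannot be attributed cleanly to ExAblate.
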